10.3.4 Endovascular Therapy

Patients will be treated with endovascular therapy system(s) (stentriever and/or aspiration catheters) currently cleared by the FDA, under their cleared indications for use, for thrombus removal in patients experiencing an acute ischemic stroke in the anterior circulation due to large vessel occlusion. Investigators will be trained to follow the published instructions for use for the endovascular therapy system used in the procedure. Deviations from the cleared time of usage must be documented as a protocol deviation. Ensure the neurointerventional devices are labeled with an outer diameter that is compatible with the inner diameter of the NOVIS NPS Arterial Sheath and attached rotating hemostasis valve.

These devices will be introduced into the vasculature via the NOVIS NPS Arterial Sheath, during this interventional step the NOVIS NPS will be set to High Flow and remain on this setting until the neurothrombectomy has been completed.

Once the endovascular therapy systems are introduced into the NOVIS NPS Arterial Sheath continuous reverse flow will be maintained throughout the interventional steps, until all other devices are removed and the thrombectomy attempt is complete.

The transcarotid intervention may be abandoned at the discretion of the treating operator. The operator will document reason for failure in patient records and study case report forms.

10.3.5 Procedural Angiography

Angiographic evaluations will be performed pre-procedure, after recanalization, and post procedure to determine level of revascularization. Angiography must be performed in the involved territory.

Prior to the start of the procedure, the mTICI scores within the vascular territory being treated should be assessed. Angiographic films of the occlusion being treated must allow clear visualization of the target artery. The same orientation should be used before and after endovascular therapy in order to allow a valid analysis of the reperfusion status of the vessel(s). These angiographic evaluations will be submitted by the sites for core lab review.

In the event of a procedural complication or adverse event, detailed angiographic images should be obtained and submitted. All adverse events that occur during the procedure must be documented and recorded on the applicable CRFs.

10.4 Post-Procedure Medications

Post-procedural medication should be administered per the institution's standard of care for endovascular therapy and should be documented on the Concomitant Medication Form.

10.5 Post-Procedure Surgical Wound Management

Surgical wound closure and management should be done per the institutional standard of care. Any significant post-procedural adverse event should be assessed and documented on the Adverse Event CRF.

11 Post-Procedure Evaluations

All enrolled patients will undergo MRI post-procedurally per the institutional standard of care. Post-procedural MRI imaging and reports will be submitted to Sponsor.

11.1 24 Hours Post-op

The NIHSS must be obtained within 24 hours (+/- 6 hours) from the end of the index procedure. This test must be performed whether or not it is considered part of the Investigator's standard of care and must be performed by neurologist or NIHSS-certified personnel. Every attempt should be made to have the same person conduct the exam at each follow-up visit. This assessor should be independent of the treating operator and patient's mechanical neurothrombectomy procedures. The primary operator of the treated patient may not perform the neurological exam.

Additionally, patients will undergo CT/CTA and CTP, per the Institution's standard of care at 24 hours to assess infarct volume, recanalization, hemorrhage, and reperfusion. The CTP imaging and report will be submitted by the sites for core lab and DSMB review.

For the 24 hours post-op time period, any changes to the patient's study medications are to be recorded from end of the index procedure up to 24 hours post-op. All Adverse Events occurring from the end of the index procedure to 24 hours post-op are to be reported. In the case of a suspected neurological event, NIHSS should be repeated as close to and prior to the 24th hour of symptom onset.

In the event of patient death prior to the 24-hour assessment, all available information regarding the primary cause of death and date/time of death will be reported. Additionally, site will report if the patient had "do not resuscitate" (DNR) or "comfort care only" status prior to expiration. All deaths must be reported to Sponsor within 24 hours of becoming aware (as per section 12).

11.2 Day 5-7 or Discharge

The patient may be discharged from the hospital when clinically stable, at the Investigator's discretion. The following neurological assessments must be obtained between Day 5-7 (if patient remains in hospital) or prior to discharge, whichever is earlier:

- NIH Stroke Scale
- Modified Rankin Scale

The neurological assessment must be performed whether or not it is considered part of the Investigator's standard of care and must be performed by neurologist or NIHSS-certified personnel. Every attempt should be made to have the same person conduct the exam at each follow-up visit. This assessor should be independent of the treating operator and patient's mechanical neurothrombectomy procedures. The primary operator of the treated patient may not perform the neurological exam.

Records of any changes to the patient's study medications are to be recorded from the 24-hour post-op visit up to discharge. All Adverse Events occurring from the 24-hour post-op visit to patient discharge are to be reported. In the case of a suspected neurological event, NIHSS should be repeated as close to and prior to the 24th hour of symptom onset.

In the event of patient death prior to the 5-7 day or discharge assessment, all available information regarding the primary cause of death and date/time of death will be reported. Additionally, site will report if the patient had "do not resuscitate" (DNR) or "comfort care only" status prior to expiration. All deaths must be reported to Sponsor within 24 hours of becoming aware (as per section 12).

11.3 Clinical Follow-up

Trained study staff at each site will review the study requirements with the patient to maximize compliance with the follow-up schedule. The trained study staff will instruct patient to return for follow-up assessments according to the study schedule of events listed in Appendix 1.

11.3.1 30 Days

The following neurological assessments must be obtained 30 days (+/- 7 days) from the index procedure:

- NIH Stroke Scale (required only for in office visits)
- Modified Rankin Scale

This visit may be completed via phone or in office visit. If a phone visit is administered, then the NIHSS will not be completed. If an in-office visit is completed both the NIHSS and mRS assessments should be completed. This visit and associated neurological assessments must be performed whether or not they are considered part of the Investigator's standard of care and must be performed by neurologist or NIHSS-certified personnel. Every attempt should be made to have the same person conduct the exam at each follow-up visit. This assessor should be independent of the treating operator and patient's mechanical neurothrombectomy procedures. The primary operator of the treated patient may not perform the neurological exam.

Records of any changes to the patient's study medications are to be recorded from discharge up to the 30-day follow-up visit. All Adverse Events occurring from discharge to the 30-day follow-up visit are to be reported. In the case of a suspected neurological event, NIHSS should be repeated as close to and prior to 24th hour of symptom onset.

In the event of patient death prior to the 30-day assessment, all available information regarding the primary cause of death and date/time of death will be reported. Additionally, site will report if the patient had "do not resuscitate" (DNR) or "comfort care only" status prior to expiration. All deaths must be reported to Sponsor within 24 hours of becoming aware (as per section 12).

11.3.2 90 Days

The following neurological assessments must be obtained 90 days (+/- 14 days) from the index procedure:

- NIH Stroke Scale
- Modified Rankin Scale

This visit is expected to be completed as an in-office visit. The neurological assessment must be performed whether or not it is considered part of the Investigator's standard of care and must be performed by neurologist or NIHSS-certified personnel. Every attempt should be made to have the same person conduct the exam at each follow-up visit. This assessor should be independent of the treating operator and the patient's mechanical neurothrombectomy procedures. The primary operator of the treated patient may not perform the neurological exam.

Records of any changes to the patient's study medications are to be recorded from the 30-day follow-up call/visit up to the 90-day follow-up visit. All Adverse Events occurring from the 30-day follow-up call/visit to the 90-day follow-up visit are to be reported. In the case of a suspected neurological event, NIHSS should be repeated as close to and prior to 24th hour of symptom onset.

In the event of patient death prior to the 90-day assessment, all available information regarding the primary cause of death and date/time of death will be reported. Additionally, site will report if the patient had "do not resuscitate" (DNR) or "comfort care only" status prior to expiration. All deaths must be reported to Sponsor within 24 hours of becoming aware (as per section 12).

If the COVID-19 Pandemic impacts the ability of the patient or site to complete this visit on-site, a remote phone visit may be done. If a phone visit is administered, then the NIHSS will not be completed.

11.4 Patient Flow Diagram

[figure not shown]

Image also provided in Appendix 5.

12 Adverse Events

Adverse event (AE) data will be collected and recorded from index procedure through 90-day follow-up period (or until patient discontinuation) for all enrolled patients on the Adverse Event CRF. At each evaluation, the Investigator or coordinator will determine whether an adverse event has occurred based on, but not limited to reports from the study patient, observed by the investigator or coordinator or documented in the medical record. For the purpose of this protocol, an adverse event is any untoward medical occurrence in a study patient, which may or may not have a causal relationship with the study device. It includes any pre-existing condition that increases in severity or frequency or any new events that occur after the index procedure. An elective procedure for a pre-existing condition (that has not worsened) is not considered an AE.

Event, date of onset, duration, severity, seriousness, treatment, outcome and relationship to the device or procedure will be recorded on the Adverse Event CRF and cross-tabulated according to:

- Severity (Mild, Moderate, Severe)
- Seriousness (Serious Adverse Event (SAE), Non-serious AE)
- Serious Adverse Device Effect (SADE)
- Unanticipated Adverse Device Effect (UADE)
- Procedure-Relatedness (Not Related, Possibly Related, Probably Related, Causal/Related)
- Device-Relatedness (Not Related, Possibly Related, Probably Related, Causal/Related)

Anticipated AEs have been listed in Section 23.1, 23.2, 23.3 & 23.4, and all AEs will be monitored until they are adequately resolved or explained at the end of the study follow-up period. Beyond the routine annual reports, interim progress report will be provided every three months to FDA.

12.1 Severity

The term “severe” is used to describe intensity (severity) of a specific event. An event itself, may be of relatively minor medical significance (such as a severe headache). This is not the same as a “serious”, which is based on an outcome usually associated with events that pose a threat to the subject’s life or functioning. (See Section 12.2 for definition of a serious adverse event.)

12.2 Serious Adverse Events

When an adverse event meets the definition for serious adverse event, it should be considered as such and reported immediately (within 24 hours) of becoming aware of the event to the Sponsor and recorded in the source documentation. The SAE should be further reported to the reviewing IRB per hospital IRB requirements. An adverse event is considered serious if the event:

- Leads to death;
- Leads to a serious deterioration in the health of the patient that:
 - Results in life-threatening illness or injury;
 - Results in permanent impairment of a body structure or a body function;
 - Requires inpatient hospitalization or prolongation of existing hospitalization;
 - Results in medical or surgical intervention to prevent permanent impairment to a body structure or a body function.

An Adverse Event form will be completed promptly and no later than 10 working days after becoming aware of the event. Reports relating to the patient’s subsequent medical course must be submitted to the Sponsor and the reviewing IRB until the event has subsided or, in case of permanent impairment, until the event has stabilized, and the overall clinical outcome has been ascertained.

12.3 Serious Adverse Device Event

Serious adverse device events are defined as a device related AEs that has resulted in any of the consequences characteristic of a serious adverse event. The Investigator will report these events within 24 hours of becoming aware of the event to the Sponsor and to the reviewing IRB per hospital IRB requirements.

Reports relating to the patient’s subsequent medical course must be submitted to the Sponsor and the reviewing IRB until the event has subsided or, in case of permanent impairment, until the event has stabilized, and the overall clinical outcome has been ascertained.

12.4 Unanticipated Adverse Device Effects

Unanticipated adverse device effects are defined as any serious adverse effect on health, safety or any life-threatening problem or death caused by, or associated with the study device; if that effect, problem, or death was not previously identified in nature, severity or degree of incidence in the study protocol and informed consent. When an adverse event meets the definition of an unanticipated adverse device effect (UADE) or that relationship is unknown, the Investigator will report the event to the Sponsor within 24 hours and provide documentation within 10 working days after the Investigator first learns of the effect and to the reviewing IRB as required.

Follow-up reports relating to the patient's subsequent medical course must be submitted to the Sponsor and the reviewing IRB until the event has subsided or, in case of permanent impairment, until the patient's condition stabilizes, and the likely overall clinical outcome has been ascertained.

12.5 Relatedness

The relationship between the use of the medical device (including the medical - surgical procedure) and the occurrence of each adverse event shall be assessed and categorized by the site Investigator. During causality assessment activity, clinical judgement shall be used, and the protocol consulted. The presence of confounding factors, such as concomitant medication/treatment, the natural history of the underlying disease, other concurrent illness or risk factors shall also be considered by the Investigator. Causality assessment will also be reviewed and adjudicated by the Clinical Events Committee.

Each AE will be classified according to four different levels of causality. The Sponsor and the Investigators will use the following definitions to assess the relationship of the adverse event to the investigational medical device or procedures:

- **Not Related:** The adverse event is determined to be solely caused by the underlying disease, disorder or condition of the study patient, or attributable solely to other extraneous causes (unrelated to the device, device malfunction or procedure).
- **Possible:** the relationship with the use of the investigational device is weak but cannot be ruled out completely. Alternative causes are also possible (e.g., an underlying or concurrent illness/ clinical condition or/and an effect of another device, drug or treatment). Cases where relatedness cannot be assessed, or no information has been obtained should also be classified as possible.
- **Probable:** the relationship with the use of the investigational device seems relevant and/or the event cannot be reasonably explained by another cause, but additional information may be obtained.
- **Causal / Related:** The adverse event is clearly caused by the use of the device, device malfunction or the procedure, as confirmed by: the event is recognized as a known event associated with the device or procedure, the event has a temporal relationship to device or procedure, the event involves the body site or organ the device or procedure is applied to or has an effect on, or event is related error in use.

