EVT for acute ischemic stroke is most commonly performed through transfemoral access. The preference for this approach is related to the compressibility of the common femoral artery, to the fact that via this approach all great vessels from the aortic arch can be catheterized and in addition, selective catheterization of the great vessel branches (internal carotid arteries for example etc.) can be performed and thus multiple potential sites of occlusion can be accessed (Jadhav et al. 2014). It should be appreciated that almost all endovascular devices were originally formulated to be inserted via a transfemoral access point in the era of coronary catheterization and angioplasty (percutaneous coronary intervention; PCI). Barriers to great vessel/carotid/vertebral/intracranial vessel access and inadequate guide catheter support can impede or prevent device delivery to the face of the thrombus. Significant peripheral vascular disease can make traditional femoral artery access either time consuming or impossible, necessitating alternative approaches or causing early termination of the thrombectomy procedure, risking a poor clinical outcome. Similarly, in patients with certain aortic arch configurations (e.g., type III or “bovine”) or with significant cervical vascular tortuosity, catheterization may be significantly delayed, and placement of large-bore guide catheters may be

impossible (Yoo et al. 2017). The presence of significant arch atheroma burden (which increases with age) renders transfemoral access risky in terms of embolization from the arch during catheter/guidewire manipulations.

Ribo et al. performed an analysis of 130 patients undergoing endovascular procedures for acute stroke which showed that 5.4% of the patients could not be successfully catheterized via transfemoral access. A negative correlation was found between time to carotid access and final recanalization; patients with difficult access had a lower rate of recanalization. Moreover, patients with difficult catheter access also had a significantly longer procedure time but similar time from symptom onset to final recanalization meaning that catheterization of the arch and great vessel origins from a transfemoral approach is the rate limiting step. Based on this study, patients with difficult catheter access had longer procedures, lower recanalization rates and poorer outcomes at 90 days(Ribo et al. 2012).

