8.3 Inclusion Criteria

1. Patients presenting with acute ischemic stroke of the anterior circulation with large vessel occlusions who are eligible for revascularization using endovascular therapies (stentriever and/or aspiration devices)
2. Occlusion of the intracranial ICA, MCA M1, proximal MCA M2, single-vessel MCA M2, dominant MCA M2, or co-dominant MCA M2 segments
3. Patient has failed transfemoral therapy (see Appendix 4 for definition), and at least 15 minutes have elapsed from groin puncture
4. Patient must meet current NOVIS Transcarotid Neuroprotection labeling requirements
 - a. Adequate femoral venous access as assessed by ultrasound
 - b. CCA reference diameter of at least 6 mm
5. Patient is \geq 18 years of age
6. Patient willing/able to return for protocol required follow up visits
7. Patient or patient's Legally Authorized Representative (LAR) has signed the study Informed Consent form
8. Imaging requirement for patients presenting within 6 to 24 hours from last known well:
 - a. < 1/3 MCA territory involvement, as evidenced by CT
 - b. Clinical Imaging Mismatch defined as one of the following on CTP:
 - i. 0-20 cc core infarct and NIHSS \geq 10 (and age \geq 80 years old)
 - ii. 0-30 cc core infarct and NIHSS \geq 10 (and age < 80 years old)
 - iii. 31 cc to \leq 50 cc core infarct and NIHSS \geq 20 (and age < 80 years old)

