10.3.2 Failed Transfemoral Therapy

For the purposes of this study, failed transfemoral therapy is defined as either a unsuccessful transfemoral mechanical thrombectomy attempt made for at least 15 minutes having elapsed from groin puncture or inadequate or prohibitive anatomy deems a transfemoral approach not possible, as determined by the operator (see Appendix 4 for definition).

Reasons for failed transfemoral therapy should be documented both on the patient's medical record and study CRFs.

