13.3 Core Lab

A central imaging core lab will be established to independently review angiographic and CTP imaging. Angiographic images will be reviewed to provide an independent assessment of the secondary efficacy endpoint of mTICI reperfusion scores at post procedure. CTP images obtained at baseline and at 24 (+/- 6) hours will be reviewed to determine volume of infarct and mismatch for DSMB assessment.

Instructions for standardized imaging and transfer will be provided to site by Sponsor. An imaging core lab charter will ensure that consistent policies and procedures are applied throughout the imaging core lab review and determination process, and will include a minimum of two core lab members. If an unresolvable disagreement is encountered, then a third member may be included or an alternative method may be used as needed.

For each enrolled subject, all images must be appropriately de-identified and submitted for core lab review. It is important that the images be saved in native DICOM format, and that all imaging sequences are sent (without pre-selecting specific frames). It is also important that the imaging sequences are captured chronologically and are clearly labeled with date and time stamps so that they can be correlated to pre-procedure, after recanalization, and post-procedure time points.

14 Statistical Methods and Sample Size

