18.1 Selection of Clinical Investigators and Sites

The sponsor will select Investigators approved by training and experience in participating in clinical trials. Up to 8 US will be recruited and selected based upon a site assessment, appropriate facilities, and the qualifications of the Primary Investigator/s. Individual Investigators will be evaluated by the sponsor based on experience with the intended procedure(s), and ability

to conduct the study according to the study protocol. Additional selection criteria may be applied in site and/or Investigator selection:

- Adequate study population to meet the requirements of the study
- Adequate time to be personally involved in the conduct of the study
- Adequate research staff and resources to support the study
- Experience in conducting studies
- Appropriate OR (hybrid or otherwise) permitting transfemoral and surgical approaches to be performed without moving the patient within the hospital
- Investigators must be individual(s) experienced with endovascular therapy AND Investigator must be a Neurosurgeon
- Investigator must be TCAR trained
- Investigator must currently perform or have hospital privileges to perform CEA.
- The facility must be certified as a Comprehensive Stroke Center through an accredited organization.
- Willingness to observe confidentiality at all times
- Compliance to protocol procedures and willingness provide Sponsor with accurate performance data in a timely fashion
- The facility must be associated with an Institutional Review Board (IRB) that satisfies all applicable regulatory requirements and conducts meetings on a regular basis.

Prior to enrolling patients, each potential Investigator must submit a current, signed and dated curriculum vitae, a completed financial disclosure form, a completed Investigator agreement and has completed Sponsor approved protocol training.

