Appendix 4. Definitions

Access Site Complication

Complication related to the vascular access site for the index procedure including but not limited to dissection, pseudoaneurysm, hematoma, arteriovenous fistula, thrombus formation, embolization and any vascular complication that may be attributed to the device AND that requires surgical repair, surgical wound revision, transfusion etc.

Adverse Event (AE)

Any unintended disease or injury or untoward clinical sign in a research patient.

CEA—Carotid Endarterectomy

A surgical procedure in which atherosclerotic plaque is removed from the diseased carotid artery.

CVA—Cerebral Vascular Accident (See definition for Stroke)

Death

Cessation of brain, cardiac, and pulmonary functions

Neurologic Death Death due to stroke or other neurologic cause.

Cardiac Death Death due to MI or other cardiac cause.

Other Death that cannot be attributed to neurologic or cardiac causes.

Device Malfunction

The failure of a device to meet any of its performance specifications or perform as intended. Performance specifications include all claims made in the labeling of the device.

Device Related Adverse Event

An Adverse Event that was directly caused by the study device (NOVIS NPS).

Distal Embolization (DE)

Embolization of pieces of the original thrombus “downstream” in the same vascular territory as the original thrombus.

Embolization to New Territory (ENT)

Any new infarct seen in the ipsilateral ACA for MCA occlusions, on CTA or MRI at the 24-hour time point compared to baseline CT or MRI.

Failed Transfemoral Therapy

Either a transfemoral mechanical thrombectomy attempt was made unsuccessfully with at least 15 minutes having elapsed from groin puncture, or there is inadequate or prohibitive anatomy deeming a transfemoral approach not possible, as determined by the operator.

Good Clinical Outcome

A measure of neurologic functional outcome with a score of 0–2 on the modified Rankin Scale (mRS), assessed at the 90-day follow-up visit.

Intracranial Hemorrhage

A hemorrhage, or bleeding within the skull

Isolated Hemisphere

Intracranial circulation that is fed only by the ipsilateral internal carotid artery and may be detected on prior CTA/MRA

Neurological Deterioration/Worsening

A 4 or more-point increase in NIHSS from baseline to discharge. Neurological worsening could be new or evolution/progression of the index stroke.

Permanent Cranial Nerve Palsy or Injury

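### Injuries from the preceding transfemoral attempt can be counted in the NOVIS safety rates, because the plan has no baseline, start point or attribution rule to separate them

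*Protocol*

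**What the plan says.** **Entry.** Inclusion criterion 3 (Protocol 8.3) reads "Patient has failed transfemoral therapy (see Appendix 4 for definition), and at least 15 minutes have elapsed from groin puncture". Protocol 10.3.2 also accepts patients in whom "inadequate or prohibitive anatomy deems a transfemoral approach not possible, as determined by the operator", and Appendix 4 agrees with 10.3.2. The first text implies a groin puncture in everyone; the other two do not.

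**Acknowledged risk.** Protocol 3.1 says that significant arch atheroma "renders transfemoral access risky in terms of embolization from the arch during catheter/guidewire manipulations". Sections 23.2 and 23.3 list dissection and hemorrhage among the risks of angiography and endovascular therapy.

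**Baselines.** Appendix 1 schedules CT/CTA, CTP and NIHSS once before the procedure and next at 24 hours. Embolization to new territory is judged on CTA or MRI "at the 24-hour time point compared to baseline CT or MRI". Symptomatic intracranial hemorrhage (SICH) is judged against the pre-procedure NIHSS (Appendix 4).

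**Window.** Protocol 10.3.3 follows events observed once reverse flow is running. Section 12 collects events from the index procedure, whose start is not defined.

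**Attribution.** Sections 12 and 12.5 grade device and procedure relatedness on four levels, with no level for the transfemoral attempt. On unclear cases: "Cases where relatedness cannot be assessed, or no information has been obtained should also be classified as possible". The primary outcome (7.1) includes complications that could be ascribed to the device and need treatment; Appendix 4 confines device-related events to those NOVIS directly caused.

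**Tabulation.** SAP 8.2.1.1 presents device-related SAEs as site-reported. SAP 8.3 puts the adjudications of the Clinical Events Committee (CEC) in a separate table. SAP 2 and 5 compare the safety rates numerically with TCAR data.

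**Reperfusion.** Protocol 10.3.5: "Prior to the start of the procedure, the mTICI scores within the vascular territory being treated should be assessed". Section 13.3 describes the core lab's task as "independent assessment of the secondary efficacy endpoint of mTICI reperfusion scores at post procedure".

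**The concern.** The study objective is the feasibility and safety of NOVIS, but in a patient with a transfemoral attempt the follow-up data describe two procedures in immediate succession. If the first leaves a dissection, an embolus or a bleed that is noticed only after the second, nothing in the plan assigns it to the first.

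The TCAR comparison patients are not described as having had a failed transfemoral attempt beforehand. The SAP's argument that SICH risks in the two populations offset one another weighs reperfusion injury, mechanical manipulation, antiplatelet therapy and heparin, but not the preceding attempt. With 30 to 40 per-protocol patients, a single wrongly assigned event visibly changes a primary safety rate. If the source of an injury is not recorded at the time, it may not be recoverable later.

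**Working it through.** **1. Can a transfemoral injury first seen later be counted?**

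| Primary event | Reference or definition | Must NOVIS be the cause? | Can it enter? |
|---|---|---|---|
| Symptomatic hemorrhage | Pre-procedure NIHSS, not timed against the attempt | No | Yes |
| Dissection from ancillary devices | 'Ancillary' undefined | No | Yes, if transfemoral tools count as ancillary |
| Device-related vascular SAE, including embolization | Protocol 7.1 and Appendix 4 set different causal tests; counting grades unstated | Yes | Depends on the unstated rule |

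Symptomatic hemorrhage is the clearest route, because no relatedness grade can remove it. Embolization to new territory is not itself a listed outcome; it matters only if the embolus is recorded as a device-related SAE.

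**2. Does the event window keep such injuries out?** Section 10.3.3 turns on when an event is observed, so an injury made earlier but seen later falls inside. One recognised during the attempt may fall outside. Section 12 depends on where the index procedure begins. Failed transfemoral therapy is described inside section 10.3, the transcarotid procedure section, so the boundary is open there too.

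**3. The plan's own figures.** The documents derive no sample size (no alpha, power or precision target), so there is none to reproduce. The ROADSTER serious-dissection rate (Protocol 3.2.2) does reproduce: 4/219 = 1.83%, stated as 1.8%.

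**4. Weight of one event**, with all subjects as denominator (SAP 8). The per-protocol range is 30 to 40 and the ITT maximum 60 (Protocol 14.2).

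| n | One event, 100/n points | Expected at 4/219, n × 4/219 | Chance of at least one, 1 − (215/219)^n |
|---|---|---|---|
| 30 | 3.3 | 0.55 | 0.425 |
| 40 | 2.5 | 0.73 | 0.522 |
| 60 | 1.7 | 1.10 | 0.669 |

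Exact (Clopper-Pearson) 95% intervals at n = 30: 0 events, 0% (0 to 11.6); 1 event, 3.3% (0.1 to 17.2); 2 events, 6.7% (0.8 to 22.1).

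**5. Sensitivity to carry-over.** The documents give no transfemoral complication rate. Assume that a share c of patients carries in an event of the same kind as the benchmark (dissection needing treatment), that all are counted, and that they occur independently of a true 4/219. The observed rate is 1 − (1 − 4/219)(1 − c):

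- c = 2%: 3.8%, or 1.14 expected events in 30
- c = 5%: 6.7%, or 2.02
- c = 10%: 11.6%, or 3.49

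**6. Reperfusion.** If a share f were already at mTICI 2b or better before transcarotid access, and success in the rest were t, the rate would rise by f(1 − t). For t, assume 60% to 84%; the upper value is the direct carotid puncture series in Protocol 3.2. An assumed f of 5% gives 0.05 × 0.16 = 0.8 to 0.05 × 0.40 = 2.0 points; f of 10% gives 1.6 to 4.0. The documents supply no f.

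**The case against.** Four stronger readings are tempting, and the documents do not support them.

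- **That doubtful events default to the device.** 'Possible' is the weakest of three related grades. Its definition allows for another device or treatment as the cause, investigators must weigh confounding treatment, and the CEC adjudicates causality. Appendix 4's direct-causation test would exclude such events. What stands is that no text says which grades count, or that CEC results replace the site-reported table.
- **That every patient had an attempt, with imaging known to precede it.** The anatomy-only limb contradicts the first part. The second is a reasonable inference from the eligibility role of the scans, but no passage times them against groin puncture. The site requirement for a room "permitting transfemoral and surgical approaches to be performed without moving the patient within the hospital" concerns capability, not scan timing. What stands is that nothing is scheduled between the two approaches.
- **That carry-over always works against NOVIS.** SAP 5 also compares symptomatic hemorrhage with thrombectomy literature, and Protocol 3.1 says thrombectomy is most commonly transfemoral. For that comparison the imbalance is not one-sided.
- **That reperfusion gained transfemorally inflates mTICI success.** Entry requires an occlusion, and a pre-procedure mTICI is already required, with the angiograms sent to the core lab. Emboli left by the attempt could equally lower the final grade. What stands is that the pre-procedure grade has no stated use and is not fixed to a moment after the attempt was abandoned.

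It is also fair that no hypothesis is tested. At the ROADSTER rate alone, 30 patients would show at least one dissection with probability 0.425, so a single event proves nothing. In addition, SAP 5 compares ancillary-device dissections with those from devices used with ENROUTE, which suggests that 'ancillary' means ancillary to the NPS, though this is not stated.

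**Conclusion.** The concern holds as a gap in definition and attribution. Followed as written, the plan can count transfemoral injuries in the NOVIS safety rates, most clearly for symptomatic hemorrhage and, depending on how 'ancillary' is read, for dissection. For device-related SAEs it depends on a counting rule that is absent.

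The size is unknown. One event is worth 3.3 points at n = 30, 2.5 at 40 and 1.7 at 60. The 3.8% to 11.6% range rests wholly on an assumed carry-over of 2% to 10% and on all carried-in events being counted. That most patients will have had an attempt is an expectation from Inclusion 3; the documents give no split. Carry-over is possible rather than certain, since events recognised before reverse flow may never be collected. A material bias in the reperfusion rate is not established.

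**What to change.** 1. Define the start of the index procedure and use it in Protocol 10.3.3, 12 and Appendix 4. State whether the pre-procedure NIHSS used for SICH precedes the transfemoral attempt.
2. Define the pre-procedure angiogram of 10.3.5 as the last run after the transfemoral approach is abandoned and before tools enter through NOVIS. Have the core lab score it for mTICI, dissection, extravasation and occlusion in a new territory.
3. Add 'related to the transfemoral attempt' to the adverse event CRF and to CEC adjudication. Limit 'ancillary devices' to those used through the NOVIS sheath.
4. State which causality grades count as device-related, reconcile 7.1 with Appendix 4, and base the primary device-SAE rate on CEC adjudication.
5. Report each primary safety rate twice: for all events, and excluding those visible on the reference run or adjudicated as transfemoral. Keeping the all-event rate ensures that no signal is hidden.
6. For reperfusion, only tabulate the pre-transcarotid against the final core-lab mTICI. Reconcile the success threshold, which SAP 7.4 gives as mTICI 2 or more and Protocol 7.2 and SAP 2 give as 2b or more.
7. Reconcile Inclusion 3 with 10.3.2 and Appendix 4, and record whether each patient had an attempt.

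The cost is one CRF field, wording changes in the protocol, SAP and the two charters, and a little more core lab and CEC work. The angiograms are already submitted, so no new imaging is needed.
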